1.3. Validation study (the second year)

1.3.1. Participants

For the relative small sample size of the present study, we analyzed all variables using non-parametric approaches. The sample size for this study was estimated using the primary outcome effects (mean posttest score) in two previously published studies.^{12,30} Using a two-tailed Wilcoxon signed-rank test for calculating the sample size (normal parent distribution; effect size, 0.8; type I error, 0.05; power, 80%), we got a sample size of 27 in each group at the minimum power of 0.80. For considering a 10% drop-out rate to fulfill the criteria of intention-to-treat analysis, we needed at least 30 participants to attend this study.

1.3.1.1. The **inclusion criteria** of the present study are:

- 1) Age > 20 years old & < 70 years.
- 2) UME students (defined as the 5 or 6 years of medical school training).

1.3.1.2. The exclusion criteria are:

- 1) Previous ORL-HNS training;
- 2) Declining to participate.

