The sample size for this study has been estimated using the primary outcome effect (change in multiple-choice test scores) among six undergraduate medical students in the system-design study: increased 43±18 [IM module] & 35±21 [PPS module]) in the pilot study. Using a two-tailed Wilcoxon signed-rank test for calculating the sample size (normal parent distribution; effect size, 0.41; type I error, 0.05; power, 80%) using G*Power 3.1.9.2 software, we get a sample size of 26 in each group at the minimum

power of 0.80. For considering an approximate 10% drop-out rate to fulfill the criteria of intention-to-treat analysis, we need at least 30 participants to attend this study. Accordingly, we estimate that a total of 60 participants included in analysis is suitable for the validation study (Part II of the present study). For better characterization and comparison of primary outcome after team discussion, we decide to use "percentage change" in addition to "change" in the future study.

Reference

- Taiwan Medical Accreditation Council. Six-years program of medical education. http://www.heeact.edu.tw/ct.asp?xItem=14388&ctNode=332&mp=3, accessed 6 December 2014.
- American Association of Medical Colleges. Recommendations for clinical skills curricula for undergraduate medical education. Executive summary. Washington, DC: American Association of Medical Colleges; 2005:3.
- Effective Use of Educational Technology in Medical Education. American Association of Medical Colleges (AAMC) Institute for Improving Medical Education. Washington 2007:3.

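### The current sample size matches a halved one-sample signed-rank calculation, so the two-arm comparison has about 30% power at the assumed effect, not 80%

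*Combined protocol and SAP*

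**What the plan says.** The section on sample size estimation in the Modified Protocol takes its assumption from pilot change scores on the multiple-choice test, "among six undergraduate medical students in the system-design study": "increased 43±18 [IM module] & 35±21 [PPS module". The method is given as "Using a two-tailed Wilcoxon signed-rank test for calculating the sample size", assuming a normal parent distribution. The settings and the result are given as "effect size, 0.41; type I error, 0.05; power, 80%) using G*Power 3.1.9.2 software, we get a sample size of 26 in each group". After an allowance of about 10% for drop-out, the section says "we need at least 30 participants to attend this study" and then "we estimate that a total of 60 participants included in analysis is suitable for the validation study".

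Section 1.3.1 of the original protocol used the same test label with a larger assumed effect: "effect size, 0.8; type I error, 0.05; power, 80%), we got a sample size of 27 in each group".

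The design is stated elsewhere. Section 1.1 describes a randomised, parallel-controlled trial. Section 1.3.2 allocates each participant 1:1 to either IM or PPS. Section 1.3.5 plans a t test, or a Mann-Whitney or Wilcoxon rank test for skewed variables.

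**The concern.** The signed-rank test compares paired values or tests one sample against a fixed value. Nothing pairs an IM student with a PPS student, so the rank test for the module comparison is Mann-Whitney.

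The numbers also give a warning. Between the two versions of the calculation the assumed effect fell from 0.8 to 0.41, with the same alpha, power and test label. Required numbers scale roughly with 1/d², so they should have risen about (0.8/0.41)² = 3.8-fold. Instead they went from 27 to 26 per group.

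At stake is how the IM-versus-PPS result is read. A reader told that the trial had 80% power for an 8-point difference could take a non-significant result as evidence that the modules perform alike. If the real power is near 30%, such a result says little about an 8-point difference.

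**Working it through.** **Inputs.** From the Modified Protocol: mean change 43 (SD 18) for IM and 35 (SD 21) for PPS; effect size 0.41; two-sided alpha 0.05; power 80%; normal parent distribution; drop-out about 10%; 60 participants in total. From Section 1.3.2: two independent arms, 1:1.

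**1. The effect size.** Pooled SD = √((18² + 21²)/2) = √382.5 = 19.56. d = (43 − 35)/19.56 = 0.409, the stated 0.41. It is not a within-arm effect; from the same figures those would be 43/18 = 2.4 and 35/21 = 1.7.

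**2. Method.** For a normal parent, a rank test behaves like a t test on n × 3/π observations (asymptotic relative efficiency 3/π = 0.955). Power then comes from the noncentral t distribution, two-sided at 0.05:

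- Signed-rank, N in total: n* = 0.955N, df = n* − 1, noncentrality = d√n*.
- Mann-Whitney, n per group: n* = 0.955n, df = 2n* − 2, noncentrality = d√(n*/2).

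**3. Reproducing the plan's 26.** Signed-rank at d = 0.41:

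- N = 50: power 79.2%.
- N = 51: n* = 48.70, noncentrality 2.861, power 80.0%.
- N = 52: n* = 49.66, noncentrality 2.889, power 80.8%.

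The requirement is 51 in total, or 52 with unrounded d = 0.409. Half of 52 is 26. The other variants tried at d = 0.41 do not give 26:

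| Calculation | Required number |
|---|---|
| Two-sample t test, two-sided | 95 per group |
| Mann-Whitney, two-sided | 99 per group (100 at d = 0.409) |
| Mann-Whitney, minimum efficiency 0.864 | 110 per group |
| Mann-Whitney, one-sided | 78 per group |
| Normal approximation, two-sided | 94 per group |
| Signed-rank, one-sided | 40 in total |

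**4. The earlier figure.** At d = 0.8 a true signed-rank calculation needs 15 in total. Mann-Whitney needs 27 per group (n* = 25.78, noncentrality 2.872, power 80.4%). The 27 in Section 1.3.1 is therefore a correct two-group figure under the wrong label. In the Modified Protocol the number itself fits only the one-sample test.

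**5. Actual power for IM versus PPS at d = 0.41.**

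| Per group | Noncentrality (Mann-Whitney) | Mann-Whitney power | t test power |
|---|---|---|---|
| 26 (stated requirement) | 1.445 | 29% | 31% |
| 27 (60 × 0.9 = 54 analysed) | 1.472 | 30% | 32% |
| 30 (all 60 analysed) | 1.552 | 33% | 35% |
| 99 | 2.819 | 80% | – |

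A simulation of the Mann-Whitney test with the pilot means and SDs gave 28% at 26 per group and 32% at 30.

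**6. Detectable difference at 80% power (Mann-Whitney).** At 27 per group: 0.796 SD, or 0.796 × 19.56 = 15.6 points. At 30 per group: 0.753 SD, or 14.7 points. The pilot difference is 8 points.

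**7. Numbers for drop-out.** 26/0.9 = 28.9, so about 30 is a per-group figure and not a trial total. For 80% power at 0.41, 99/0.9 = 110 per group, 220 in total.

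**The case against.** Several points can be made for the plan.

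- **How 0.41 arose and whether 26 is a halved total are inferred.** This stands. The section shows neither step. A paired effect with an assumed correlation of 0.5 would be 8/√(18² + 21² − 18 × 21) = 0.407, which also rounds to 0.41. But the trial is unpaired, and no two-group test gives 80% power at 0.41 with 26 per group, whatever the route to 26.
- **The power is conditional on 0.41, which rests on six students.** This also stands. If the six were split three and three (an assumption), a rough 95% interval for d runs from about −1.2 to 2.0. The plan's 80% carries the same condition, so the imprecision does not support it. The SD used to express detectable differences in points is equally uncertain.
- **The 27 and the 26 come from different protocol versions.** True. The later calculation replaces the earlier one, so the comparison is a warning sign and not a contradiction within one plan.
- **Analysing all 60 is compatible with intention-to-treat.** It is, though no method for missing posttests is stated. With all 60 analysed, power is still only 33%.
- **Thirty as a total is a slip.** Agreed; the next sentence gives 60.
- **The primary outcome can be read as change within each arm.** For that, effects of 2.4 and 1.7 give power near 100%. The shortfall is confined to the between-module comparison. The sample size section sets out the two modules' changes and counts participants per group, and 0.41 is not a within-arm effect. Even a signed-rank test on 26 at 0.41 has only 50% power.

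The SDs are already those of the change, so no pre-post correlation is missing. Adjusting for the pretest might raise power, but no such analysis is planned.

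**Conclusion.** The concern holds. The stated 26 per group does not give 80% power for IM versus PPS at an effect of 0.41. It gives about 29%, and the 60 participants planned give 30% to 33%, depending on whether 54 or all 60 are analysed. About 99 per group would be needed.

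This assumes two independent arms, two-sided alpha 0.05, normally distributed change scores and a true effect of 0.41. Using a t test instead adds about two percentage points. That the 26 is a halved signed-rank total is the likely explanation, but the conclusion does not depend on it. The test label in Section 1.3.1 and the wording about 30 and 60 participants are minor by comparison.

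**What to change.** Keep 60 participants and replace the power statement in the Modified Protocol with a calculation for two independent groups, for example:

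*Thirty participants will be randomised to each group. With about 27 per group analysed after 10% drop-out, a two-sided Mann-Whitney test at the 0.05 level has 80% power for a difference of about 0.80 SD (about 16 points on the pilot SD of 19.6). Power for the pilot effect of 0.41 is about 30%. The pilot estimates come from six students and are imprecise.*

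Also:

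- Name the Mann-Whitney test as the basis of the calculation, and correct or annotate the same label in Section 1.3.1.
- State that 30 is a per-group number.
- Drop the statement that 60 will be in the analysis, or say how participants without a posttest will be kept in it.
- State that a non-significant IM-versus-PPS result does not exclude an 8-point difference.

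The cost is wording, and a less favourable but accurate power statement. No participants are added. The alternative of powering for 0.41 would need about 220 enrolled, while the section on anticipated problems puts the available students at roughly 150 a year.
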